## 4.0 OVERVIEW OF STUDY DESIGN/INTERVENTION

### 4.1 Design

#### Study Design

This is a single center, single blind, prospective, randomized, phase II controlled trial to be conducted without crossover.

#### Trial Arms

Patients will be randomized to one of two arms designated **Bead Arm** and **Bead + Dox Arm**, where the planned interventions are:

- **Bead Arm:** Hepatic arterial embolization with Bead Block microspheres, beginning with 100 – 300 micron beads, and using larger particles if necessary until stasis is evident.
- **Bead + Dox Arm:** Hepatic arterial embolization with 100-300 micron drug eluting microspheres (LC Bead) loaded with 150 mg Doxorubicin, followed by embolization with Bead Block microspheres (100-300 micron and larger size beads as necessary) until stasis is evident.

#### Limitations of Study Design

It is not possible to perform the embolization procedure in a completely double blinded fashion. Doxorubicin is red, and when added to the embolization beads results in red colored spheres, thus the interventional radiologist performing the embolization will know which embolic agent is being used. Subsequently, CT readers assessing response to treatment, and TTP will be blinded to the treatment method.

#### Tumor Response

For the purposes of the primary objective, the triple phase CT obtained within 2-3 weeks of initial treatment will be used to assess response to treatment. Tumor response will be catalogued according to RECIST criteria as well as by % necrosis determined using the study CT volumetric method.

#### RECIST Response Criteria

RECIST criteria responses are defined as follows:

Complete Response (CR):	disappearance of all target lesions (up to 10 target lesions)
Partial Response (PR):	$\geq 30\%$ decrease from baseline
Stable Disease (SD):	All other cases
Progressive Disease (PD):	$\geq 20\%$ increase from the smallest sum of measurements since the start of treatment
Objective Response:	CR and PR

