### **Time to Progression**

Time to progression (TTP) will include and be categorized as time to: local tumor progression (LTP), distant hepatic progression (DHP), and extra-hepatic progression (EHP). Local tumor progression (LTP) will be measured as the time from randomization until the first measurement of progression as determined by the central reading group using RECIST criteria as well as volumetric criteria for the target tumor. Local tumor progression (LTP) will be defined specifically as  $\geq 20\%$  increase from the smallest sum of measurements since the start of treatment (RECIST criteria, see above), or  $\geq 75\%$  increase in enhancing tumor volume. Distant hepatic progression (DHP) will be defined as the development of any new discontinuous disease within the liver, and the development of any extra-hepatic disease will constitute extra-hepatic progression (EHP).

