#### **Tumor Response**

Tumor response will be measured according to RECIST criteria, as well as using the new volumetric method of assessing non-viable tumor. In the case of differences between these criteria, the RECIST criteria will be used for clinical judgment and decisions.

RECIST criteria responses are defined as follows:

Complete Response (CR):	disappearance of all target lesions (up to 10 target lesions) confirmed at $\geq 4$ weeks
Partial Response (PR):	$\geq 30\%$ decrease from baseline
Stable Disease (SD):	All other cases
Progressive Disease (PD):	$\geq 20\%$ increase from the smallest sum of measurements since the start of treatment
Objective Response:	CR and PR

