### **Local Tumor Response**

Local tumor response will be determined for the initial tumor volume treated following each complete treatment and be recorded as CR, PR, SD, or PD by RECIST and volumetric methods. New tumor developing in a distant previously untreated area of the liver will be considered new hepatic progression (NHP)

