## **14.0 BIOSTATISTICS**

This primary objective of this study is to estimate the response rates (CR + PR) to treatment following hepatic arterial embolization of hepatocellular cancer (HCC) using microscopic beads + Doxorubicin and beads alone by conventional RECIST criteria. With 50 patients in each arm response rates can be estimated to within +/- 14%. Patients will be randomly assigned to one the two treatment arms. A two-arm study was deemed necessary because there was not sufficient preliminary data on the control arm to design a single-arm study with historical controls. This is not a study where the goal is to test a hypothesis, rather the emphasis is on the estimation of response rates in the two arms. For this reason the sample size justification is provided in terms of the precision (half length of the asymptotic confidence interval) of these estimates instead of a power calculation. This is in the same spirit with most randomized Phase II trials of chemotherapeutic agents.

Randomization will be performed using the Clinical Research Database (CRDB), the central computing facility for clinical research at MSKCC. This system will generate a treatment assignment using the method of permuted blocks, at the time the patient is registered. Due to the nature of the treatment, the interventional radiologist will not be blinded but the radiologists assessing response to treatment will be blinded to treatment assignment.

One of the secondary objectives is to quantify the amount of necrosis in the two treatment arms and correlate this with conventional RECIST response as well as time to progression. With 50 patients in each arm, percent necrosis can be estimated to within +/- 14% of its standard deviation. Using 50% necrosis as threshold we plan to evaluate the degree of agreement between RECIST and necrosis response using Cohen's kappa and McNemar's test.

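### The response tables have no new-lesion rule, so one CT can count as an objective response in the primary endpoint and as a progression event in TTP

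*Combined protocol and SAP*

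**What the plan says.** Section 14.0 sets the primary objective: to "estimate the response rates (CR + PR) to treatment following hepatic arterial embolization of hepatocellular cancer (HCC", by arm. Section 4.1, Tumor Response, fixes the scan: "the triple phase CT obtained within 2-3 weeks of initial treatment will be used to assess response to treatment".

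The classification is in the table under RECIST Response Criteria in Section 4.1 and is repeated under Tumor Response in Section 12.0. CR is "disappearance of all target lesions (up to 10 target lesions". PR is a decrease of at least 30% from baseline. PD is a 20% or greater "increase from the smallest sum of measurements since the start of treatment". SD takes every remaining case, and objective response is CR plus PR. The Section 12.0 version adds a confirmation requirement to CR ("disappearance of all target lesions (up to 10 target lesions) confirmed at" four weeks or more). Neither version mentions new lesions.

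The other passages that deal with new tumor or progression are:

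- Section 4.1, under Time to Progression, lists the components of the endpoint: "Time to progression (TTP) will include and be categorized as time to: local tumor progression (LTP), distant hepatic progression (DHP), and extra-hepatic progression (EHP". Further, "Distant hepatic progression (DHP) will be defined as the development of any new discontinuous disease within the liver", and any disease outside the liver is EHP.
- Section 12.0, Local Tumor Response: the initially treated volume gets its own CR, PR, SD or PD, and "New tumor developing in a distant previously untreated area of the liver will be considered new hepatic progression (NHP".
- Section 4.1, Duration of Objective Response: a response lasts until progression by the RECIST criteria.

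**The concern.** The tables are introduced as the definitions of response, and the SD row catches whatever the other rows leave out. They are therefore not merely silent on new tumor: they assign a patient with new tumor to CR, PR or SD according to the target measurements alone. The TTP definition calls the same finding progression.

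Two things are at stake. First, the primary response rate can include patients who have progressed by the trial's own TTP definition. Second, a recorded response can run on past the appearance of new tumor, because the event that ends it is tied to RECIST progression. The conflict also bears on a stated secondary aim, in Sections 2.0 and 3.0: relating initial imaging response to TTP and judging it as a possible surrogate. That analysis needs an explicit rule on whether one scan can supply both a response and a progression.

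**Working it through.** **The plan's own figure.** Section 14.0 gives 50 patients per arm and a precision of ±14%, described as the half length of an asymptotic confidence interval. The level is not stated; 95% two-sided is assumed. Half-width = 1.96 × √(p(1 − p)/n). At the worst case p = 0.5 and n = 50 this is 1.96 × √(0.25/50) = 0.1386, or 13.9 points. The figure reproduces, and as a worst case it holds under either definition of response.

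**Applying the two rules to the same scan.** The cases are hypothetical and test only the logic.

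| Primary-endpoint CT | Response table | Time to Progression |
|---|---|---|
| Targets −35%, new tumor | PR | Event (DHP or EHP) |
| All targets gone, new tumor | CR | Event (DHP or EHP) |
| Targets −10%, new tumor | SD | Event (DHP or EHP) |
| Targets −35%, no new tumor | PR | No event |

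The first two rows are objective responses and progression events at once. The third does not affect the response rate, but it understates PD. The CR confirmation in Section 12.0 does not remove the conflict: an unconfirmed disappearance of all targets still meets the 30% decrease for PR, which needs no confirmation in either table.

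**Whether new tumor could appear by then.** The response CT follows completed treatment by 2–3 weeks (Section 10.0), but the baseline CT may precede registration by up to 6 weeks (Sections 8.0 and 12.0), and staged patients have their second session 2–6 weeks after the first (Section 9.0). Baseline to response CT can therefore reach 6 + 3 = 9 weeks with one session and 6 + 6 + 3 = 15 weeks with two, before any delay between registration and the procedure. New tumor is possible in that window; its frequency is not given.

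**Size.** One reclassified responder moves an arm's rate by 1/50 = 2 points. With 0 to 3 such patients per arm (assumption), the shift is 0 to 6 points. As an illustration, from an assumed 15/50 = 30% (half-width 12.7 points), removing 1, 2 or 3 responders gives 28%, 26% or 24%, with half-widths of 12.4, 12.2 and 11.8 points.

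**The case against.** **The protocol relies on conventional RECIST, and the table is shorthand.** Sections 2.0, 12.0 and 14.0 do name conventional RECIST, and the investigators may have intended a new-lesion rule. But Section 12.0 sends the reader back to Section 4.1 for the criteria, no RECIST version is named, and the bibliography lists no RECIST publication. The protocol's own account also varies: Section 3.0 describes a bi-dimensional product, Section 12.0 uni-dimensional measurements. Readers cannot be left to supply an unwritten rule.

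**The split between treated and new tumor is deliberate.** In a locoregional trial, shrinkage of the embolized tumor and new disease elsewhere can both be true, and the documents record new disease as DHP, NHP or EHP. This is the strongest argument. It supports keeping a local response measure, which Section 12.0 already has. It does not say how new tumor affects the primary response, which is nowhere labeled as local.

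**The read is early and the effect small.** This stands. A conflict needs both 30% shrinkage and new tumor on one early CT, and zero cases is compatible with the documents.

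**A new-lesion rule has its own cost for the correlation.** This also stands. Under that rule, a new lesion on the response CT both removes responder status and is the TTP event, which ties predictor to outcome.

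**The edit is not complete.** It does not settle progression of non-target lesions, and the anatomical coverage of the CT, which matters for EHP, is not stated. Both are fair limits; neither removes the conflict.

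**Conclusion.** The conflict is real on the written text: the response tables and the TTP definition give opposite results for a patient with at least 30% target shrinkage and new tumor on the 2–3 week CT, and new tumor does not end a response as duration is now defined. The effect on the primary rate is 2 points per case, or 0 to 6 points per arm if there are 0 to 3 cases. That count is an assumption.

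A reader might infer more, without support from the documents:

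- That the reported rate is materially inflated. The frequency is unknown and may be zero.
- That one arm is favored. The response readers are blinded, and nothing indicates a direction.
- That the response–TTP correlation is distorted in a known direction. None can be shown, and the overall rule brings a dependence of its own.
- That the ±14% is wrong. It is unaffected.

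This is a definitional gap in the primary endpoint that should be closed, not a flaw that invalidates the design.

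**What to change.** - In the response tables of Sections 4.1 and 12.0, for the primary overall response, add *and no new lesions* to CR, PR and SD, and *or any new lesion* to PD.
- Apply the same rule under Duration of Objective Response, so that new tumor ends a response.
- Use one term for new liver tumor; Section 4.1 now says DHP and Section 12.0 says NHP.
- Keep the target-only classification in Section 12.0 as a separately reported local response, and use it as a sensitivity analysis in the response–TTP correlation, because of the overlap described above.

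The cost is a few lines of text, one further tabulation and one sensitivity analysis. The response rate may come out slightly lower. The treatment-failure and re-treatment rules have their own criteria in Sections 10.0, 12.0 and 13.0 and are not changed by this edit.

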### **Measurement of Treatment Response**

Contrast enhanced CT and MRI are the best currently available methods of evaluating response to treatment for HCC, and the most reproducible means of measuring target lesions and assessing necrosis. Triple phase contrast enhanced CT scans will be performed 2-3 weeks after the first complete treatment. Patients will be grouped according to RECIST criteria; however the volumetric assessment will use a continuous scale of percent tumor necrosis.

### **Verification of Tumor Response**

Tumor response assessments will be recorded in CRDB. Triple phase CT scans will be read from PACS workstation by independent readers without knowledge of the treatment group or investigator opinion. Tumor response will be classified by RECIST criteria, as well as by volume of enhancing tumor.

### **Local Tumor Response**

Local tumor response will be measured following each complete treatment. Local tumor progression (LTP) will be recorded when the patient develops  $> 20\%$  increase in sum of uni-dimensional measurement (RECIST), or  $> 75\%$  increase in volume of enhancing tumor since beginning treatment.

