## **Time 0 + 10-14 weeks**

Patients will be seen in clinic and have vital signs evaluation (weight, blood pressure, temperature, and heart rate), CBC, chemistry profile with liver function tests, coagulation studies, AFP level, and ECOG assessment. They will have a triple phase CT scan. This CT scan will be used to determine if the patients need re-treatment. Patients with evidence of persistent or progressive tumor but who do not meet the criteria for treatment failure, will be re-treated within their original treatment arm within 6 weeks of this follow-up scan. The patients will be re-treated with same embolic agent used for first treatment, with embolization protocol identical to that outlined above. They will then re-enter the follow-up pathway.

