## **12.0 CRITERIA FOR THERAPEUTIC RESPONSE/OUTCOME ASSESSMENT**

All patients will undergo contrast enhanced triple phase CT within 6 weeks of registration and then again within 2-3 weeks of completing their first treatment. Prior to treatment index lesions according to RECIST will be identified and conventional uni-dimensional measurements obtained blinded to the patients treatment group assignment. Response to treatment will be assessed by conventional RECIST criteria (see **Section 4.1**). The electronic data will then be sent to an independent imaging laboratory where an imager not familiar with the same patient's initial data set will create a volumetric profile including volume of tumor and volume of necrosis at time 0. On the initial post-treatment scans the index tumor(s) will once again be identified and measured by an imager blinded to the patient's treatment group, and once again the electronic data will be sent to the imaging laboratory where it will be independently analyzed volumetrically, once again recording tumor volume, and volume of necrosis. These results will be recorded in the electronic database. These linear and volumetric assessments will be repeated each time the patient is imaged for the duration of the study. Any increase in standard manual measurements of >20%, or the development of > 75% increase in enhancing tumor volume will be considered evidence of progression of disease (PD) and so recorded. In addition, patients who develop  $\leq 5\%$  necrosis, by volume, following the initial treatment, or increase of >50% in sum of uni-dimensional measurements following subsequent treatments will be considered treatment failures.

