### **Volumetric Imaging Method**

We have developed a system with a practical user interface that allows operator to synchronically view baseline and corresponding follow-up images of the liver side-by-side, semi automatically delineate tumor contours, and segment necrosis with an optimal threshold determined by observing segmentation results while varying thresholds or setting a system wide threshold value. If a segmentation result is suboptimal, the system allows the operator to make manual correction (Fig 2).

[figure not shown]
**Figure 2** An image processing system allows manual segmentation of liver tumor (with blue border) and tumor necrosis (area in red). Segmented tumor contours and necrosis areas are superimposed on baseline (left) and follow-up (right) CT images. Tumor volume increased 29.5%, whereas ratio of tumor necrosis volume to tumor volume increased 388.8%.

Segmented tumor contours and necrosis areas are superimposed on baseline (left) and follow-up (right) CT images. Tumor volume increased 29.5%, whereas ratio of necrosis volume to tumor volume increased 388.8%.

In addition to the manual segmentation and semi-automated segmentation, we plan to develop a fully automated segmentation algorithm for separating tumor from normal hepatic parenchyma as well as necrosis from tumor. These are extremely difficult segmentation tasks, because 1) the intensity contrast between tumor and liver parenchyma can be very low, and 2) necrosis can be heterogeneous throughout the tumor and may be difficult to be distinguished from hypointense portions of the tumor.

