#### **Automated/Semi-Automated Segmentation of Necrosis**

Once a tumor is delineated, necrosis inside the tumor needs to be detected and segmented. As necrosis will not be enhanced by the contrast material, it appears low attenuation and possesses a certain low range of intensity on contrast-enhanced CT images. We determine this intensity range through manually extracting necroses in a large number of liver tumors and calculating the mean and standard deviation (std) of the necroses' intensity. A fixed threshold can then be determined by the equation:  $Thr = \text{mean} + a * \text{std}$ , where  $a$  is a parameter that needs to be optimized in the study. Any voxel in the tumor having an intensity value lower than  $Thr$  will be considered as a necrosis voxel. This value may be modified on a scan or patient basis and will be visually validated by the Radiologist. Volumetric tumor size and necrosis can therefore be calculated simply for an entire tumor or series of tumors.

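### The 75% enhancing-volume progression rule has no settled reference volume; read against the pre-treatment volume, it makes volumetric time to progression lengthen with early necrosis by definition

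*Combined protocol and SAP*

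**What the plan says.** The 75% enhancing-volume rule appears three times.

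- Section 4.1, Local Tumor Response: more than 75% "increase in volume of enhancing tumor since beginning treatment".
- Section 4.1, Time to Progression, which is offered as the specific definition of local progression: at least 75%, no reference volume. The diameter limb in the same sentence is an "increase from the smallest sum of measurements since the start of treatment (RECIST criteria, see above"; the bracket closes before the volume limb begins.
- Section 12.0, opening paragraph: "Any increase in standard manual measurements of >20%, or the development of > 75% increase in enhancing tumor volume will be considered evidence of progression". No reference is given for either limb.

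Local Tumor Response in Section 12.0 also records volumetric progression, with no threshold or reference. Nadir wording occurs only for RECIST sums: in the response tables of Sections 4.1 and 12.0 and in Time to Progression. The Local Tumor Response text of Section 4.1 and the opening of Section 12.0 omit the nadir for the RECIST limb as well, and use > 20% where the other places use ≥ 20%.

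The Secondary Objectives (Section 2.0) plan to correlate early necrosis with TTP by RECIST or by the volumetric method. Section 14.0 repeats the necrosis–TTP aim, and Section 3.0 wants to judge surrogacy from such correlations.

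**The concern.** Two analysts with the same scans could date volumetric progression differently, because the text does not fix the volume against which 75% is measured.

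One natural reading has a further consequence. Section 12.0 explains that necrosis does not enhance, so early necrosis lowers enhancing volume directly. If progression is measured against the pre-treatment volume, a tumour with more necrosis must regrow further before it counts as progressed. Necrosis is then part of the definition of volumetric TTP. A positive correlation between the two could appear even if necrosis had no bearing on regrowth, and could be taken as support for necrosis as a surrogate.

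**Working it through.** The plan states no sample size, event count or power that depends on this reference, so there is no plan figure to reproduce.

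**1. Regrowth needed.** Set pre-treatment enhancing volume to 1 and let f be the fraction left after treatment. A pre-treatment reference needs volume 1.75, so the fold-increase from nadir is 1.75/f. A nadir reference needs 1.75 whatever f is.

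| f | Pre-treatment reference | Nadir reference |
|---|---|---|
| 100% | 1.75/1.00 = 1.75 | 1.75 |
| 75% | 1.75/0.75 = 2.3 | 1.75 |
| 50% | 1.75/0.50 = 3.5 | 1.75 |
| 25% | 1.75/0.25 = 7.0 | 1.75 |

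Example: 100 mL falls to 25 mL. The pre-treatment rule calls progression at 175 mL, the nadir rule at 1.75 × 25 = 43.75 mL. Regrowth to 100 mL is not progression under the first rule.

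**2. Relation to the diameter rule.** For a sphere, 1.2³ = 1.728, so 75% in volume is close to 20% in diameter, which the plan measures from nadir. Conversely 1.75^(1/3) = 1.205, so for one fully enhancing sphere the volume limb cannot fire before RECIST. That fails for several lesions (the response table allows up to 10 targets). With diameters of 6, 2, 2 and 2 cm and the first growing to 7.4 cm, the diameter sum rises (7.4+2+2+2)/12 = 1.117, or 12%, but volume rises (7.4³+24)/(6³+24) = 1.788, or 79%.

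**3. Size of the built-in correlation.** Null simulation in which necrosis is unrelated to regrowth. Assumptions, none from the documents: f uniform on 0.25–1; doubling time lognormal, median 4 months, log-SD 0.3/0.5/0.8. Scans follow the plan's schedule, and re-treatment starts after the 10–14 week scan. Censoring, removal for treatment failure and distant or extra-hepatic progression are not modelled. Spearman correlation of early necrosis with volumetric TTP:

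- Pre-treatment reference, no re-treatment: 0.73/0.56/0.39.
- With re-treatment, two treatments in total: 0.51/0.39/0.28.
- With re-treatment, three in total: 0.42/0.32/0.23. Median doubling times of 3 and 6 months give 0.46/0.36/0.25 and 0.41/0.30/0.22.
- Nadir reference, volumes read without error: 0.00.

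Adding independent competing progression (assumed exponential, mean 8–12 months) cut a pre-treatment-reference correlation of 0.45–0.50 to 0.15–0.31. A variant with mean 10 months gave about 0.1.

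**4. Limits of a nadir rule.**

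- Read error: with an assumed 20% proportional error the correlation is -0.22/-0.19/-0.15 without and -0.19/-0.16/-0.11 with re-treatment. At 10% it lies between about -0.10 and -0.03.
- Early regrowth: if regrowth starts at embolization and necrosis is read at 2.5 weeks, the error-free nadir rule gives +0.06/+0.12/+0.22.
- Volume near zero: suppose true enhancing volume is zero at two scans, with independent normal additive read errors of equal spread and negative reads set to zero. The second read shows at least a 75% increase with probability 1/4 (first read zero, second positive) plus arctan(1/1.75)/(2π) = 0.083 (both positive), or about 33%, with no regrowth at all.

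**The case against.** A reader might infer that the plan prescribes a pre-treatment reference for volume while using a nadir for RECIST. The documents do not support that. In Local Tumor Response (Section 4.1) the closing phrase covers both limbs, and it may mark a time window. That text and the opening of Section 12.0 also leave out the nadir for RECIST, which other sections state clearly. They may be shorthand for both limbs. This objection stands: what is established is an unsettled reference, and the built-in correlation follows on only one reading.

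It is also fair that time until enhancing burden exceeds its pre-treatment level by 75% is a coherent endpoint, and that longer times after deeper debulking are partly what it measures. The difficulty arises only when that time is correlated with necrosis as evidence of surrogacy.

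The consequence is narrow. Stand-alone volumetric TTP is named in one secondary objective. The overall TTP definition also includes nadir-based RECIST, distant hepatic and extra-hepatic progression, which dilute the effect. Re-treatment weakens it further: at the 10–14 week visit (Section 10.0), those showing "evidence of persistent or progressive tumor but who do not meet the criteria for treatment failure, will be re-treated within their original treatment arm". Section 12.0 lets RECIST settle differences between the criteria for clinical decisions, but that does not say how volumetric TTP is dated.

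Finally, a nadir rule is not neutral, as step 4 shows. A reader might infer that an association seen under both definitions cannot be an artefact. That is unsafe, because both can be positive when regrowth begins before the 2–3 week scan.

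**Conclusion.** The concern holds as an inconsistency with a conditional consequence. The three statements of the rule differ in reference and operator, and none gives a nadir for volume. If the reference is the pre-treatment volume, the direction of the effect follows from algebra: the regrowth needed is 1.75/f, so volumetric TTP rises with early necrosis at any given growth rate.

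The size is not fixed by the documents. Under the assumed growth rates the induced correlation is about 0.4–0.7 without re-treatment and 0.2–0.5 with it. It falls to about 0.1–0.3 when competing progression is added.

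A reader might go further and infer that all TTP results, or the trial's main conclusion, are compromised. They are not: the primary response rate, RECIST-TTP and survival do not use the volume reference, and Section 14.0 describes the time-to-event aim as mainly preliminary. The point still deserves correction before analysis, because the surrogacy aim is named in the plan and the remedy is cheap.

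**What to change.** For endpoint dating only, leaving clinical decisions as the plan has them:

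1. State one volume rule in Local Tumor Response and Time to Progression (Section 4.1) and in the opening of Section 12.0: an increase of at least 75% over the smallest enhancing tumour volume recorded since treatment began. Add a prespecified minimum absolute volume increase, so that the rule is defined when enhancing volume is near zero after complete necrosis. The documents give no read-error figure from which to set it, so the sponsor should base it on reader repeatability.
2. Restore the nadir reference and a single operator for the RECIST limb in Local Tumor Response (Section 4.1) and the opening of Section 12.0.
3. Report RECIST-TTP and volumetric TTP separately, and give the pre-treatment version of the volume rule as a sensitivity analysis.
4. State that an association of necrosis with volumetric TTP is not independent evidence of surrogacy; rest that on RECIST-TTP and survival. Say also that agreement between the two volume definitions does not exclude an artefact.

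The cost is wording in three places, one threshold to choose and one extra analysis. No new scans or reads are needed: "These linear and volumetric assessments will be repeated each time the patient is imaged for the duration of the study". The downside is greater sensitivity to read error, a real risk here. On contours, "If a segmentation result is suboptimal, the system allows the operator to make manual correction"; on the necrosis threshold, "This value may be modified on a scan or patient basis and will be visually validated by the Radiologist".
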